4.1 Inclusion Criteria

A subject must meet all of the following inclusion criteria to be eligible for participation in the study:

1. Male or female subjects at least 40 years of age
2. Can understand the nature of the study and protocol requirements and provide written informed consent
3. Is able to demonstrate the ability to complete subject-reported outcome measures on a handheld device, and can be reliably rated on assessment scales (in the opinion of the Investigator)
4. Must be able to designate a caregiver or study partner who the subject agrees can provide reliable information on the subject's well-being, and is willing to provide written informed consent, and to attend clinic visits with the subject

5. Has a Schwab & England ADL Scale score of 40-80% (inclusive) at both Visit 1 (Screening) and Visit 2 (Baseline) as it relates to their PDP symptoms
6. Has a Mini-Mental State Examination (MMSE) score ≥ 19 at Screening
7. *This criterion has been deleted; please consult the Summary of Changes for details.*
8. Has a diagnosis of idiopathic Parkinson's disease (PD), according to the Movement Disorders Society criteria for the diagnosis of PD ([Postuma et al. 2015](#)), without any other known or suspected cause of parkinsonism. History of initial PD symptoms onset greater than 1 year prior to Screening
9. Has psychotic symptoms that may impair function and are severe enough to warrant treatment with an antipsychotic agent
10. Has a CGI-S score of ≥ 4 when assessing psychosis symptoms at Visit 1 (Screening) and Visit 2 (Baseline)
11. If the subject is on anti-Parkinsonian medication, they must be on a stable regimen for 2 months prior to Baseline and not planning (at the time of the Baseline visit) to make a change in dose(s)
12. *This criterion has been deleted; please consult the Summary of Changes for details.*
13. *Psychotic symptoms developed after the onset of symptoms of PD*
14. Psychotic symptoms present for at least 1 month overall (could be intermittent), with active psychotic symptoms in either of the last 2 weeks prior to screening
15. Has clear sensorium at study entry (i.e., oriented to time, person, and place) in the opinion of the Investigator
16. If the subject is female, she must not be pregnant or breastfeeding. She must also be of non-childbearing potential (defined as either surgically sterilized or at least 1 year postmenopausal) OR must agree to use TWO clinically acceptable methods of contraception

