9.5 Statistical Analyses

All safety and efficacy measures will be summarized using descriptive statistics.

For continuous variables, the following summary statistics will be provided: number of subjects, mean, standard error of the mean, standard deviation, minimum, maximum, and median. For categorical variables, summaries will include the number and percentage of subjects in each category, using the number of subjects with non-missing values as the denominator for the percentages (unless otherwise specified).

All efficacy analyses will be based on the Full Analysis Set. All confidence intervals will be 2-sided 95% CIs, unless stated otherwise.

Baseline is defined to be the last non-missing value prior to the first dose of study drug.

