### 3 STUDY DESIGN

#### 3.1 General Study Design

This study will be conducted as a 16-week, multi-center, single-arm, open-label study. Pimavanserin (ACP-103) will be administered at a dose of 34 mg to approximately 53 subjects with PDP. Approximately 42 subjects are expected to complete the study, assuming a 20% drop-out rate. Approximately 25 sites in the US will participate in this study.

The duration of participation for individual study subjects will be up to 26 weeks, consisting of the following 3 periods:

[figure not shown]
- Screening period (3-35 days)
- Treatment period (16 weeks)
- Safety follow-up period (30-34 days)

The study will be conducted on an outpatient basis with visits performed at Screening, Baseline (Week 0), Week 2, Week 4, Week 8, Week 12, Week 16 (end of Treatment Period) and Follow-up (at least 30 days and not to exceed 34 days after last dose of study drug). The first dose of study drug (pimavanserin) should be taken on the morning of the day after the Baseline visit.

The study start date is defined as the date the first subject is enrolled, which is the baseline visit date for the first subject. The primary completion date is the last date that subject data was collected for the primary outcome measure. The study completion date is defined as the last date that subject data was collected, which includes the safety follow-up telephone call visit.

[Figure 1](#) illustrates the study design.

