### 5.1 General Data Reporting Conventions

For continuous variables, the following summary statistics will be provided: number of subjects, mean, standard error (SE) of the mean, standard deviation (SD), minimum, maximum, and median. Unless specified otherwise, means, medians, and confidence intervals (CIs) will be presented to one more decimal place than the raw data, and the SDs and SEs will be presented to 2 more decimal places than the raw data. In general, the maximum number of decimal places is 4 and values will be truncated to 4 decimal places in situations where there are more than 4 decimal places. Wherever possible data will be decimal aligned.

For categorical variables, summaries will include the number and percentage of subjects in each category; the number of subjects and the percentage of subjects with missing data will be summarized for demographic and baseline characteristics (if applicable). Categories with zero counts will not have zero percentages displayed. Percentages will be presented to 1 decimal place. For demographic (except for Childbearing Potential) and baseline summaries (except for NPI-Q distress), percentages will be calculated by using the total number of subjects as the denominator.

Unless specified otherwise, all statistical tests will be 2-sided hypothesis tests performed at the significance level of 0.05 for main effects. All CIs will be 2-sided, 95% CIs, p-values will generally be presented to 4 decimal places, and p-values less than 0.0001 will be presented as <0.0001

Values that are collected with “<” or “>” signs will generally be analyzed as the numerical value without the sign in tables and figures. In listings, these data will be reported as collected with the sign.

Duration in months will be calculated as (number of days/365.25)\*12 and will be rounded to 1 digit after the decimal point (tenths) for presentation purposes.

Duration in years will be calculated as number of days/365.25 and will be rounded to 1 digit after the decimal point (tenths) for presentation purposes.

Baseline is defined as the last non-missing value prior to the first dose of study drug. All change from baseline endpoints are calculated as the value of the corresponding post-baseline visit minus the value at baseline.

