### 12.2 Secondary Efficacy Endpoints

The secondary efficacy endpoints are the following:

- Change from Baseline to Week 16 on the Schwab and England ADL Scale (Caregiver and Patient version)
- Change from Baseline to Week 16 on the MDS-UPDRS Parts I total score and MDS-UPDRS Part II total score (Caregiver and Patient version)
- Change from Baseline to Week 16 on the CGI-S score for hallucinations and delusions
- Week 16 CGI-I score for hallucinations and delusions
- Week 16 PGI-I score for hallucinations and delusions

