## 12.8 Mixed Model Repeated Measures (MMRM)

The MMRM method with restricted maximum likelihood estimation (REML) will be used for selected efficacy endpoints. The dependent variable will be the change from Baseline. The independent variables in the model will include effects for visit, Baseline score, and Baseline score-by-visit-interaction. An unstructured covariance matrix will be used to model the within patient errors, and the Kenward-Roger approximation will be used to adjust the denominator degrees of freedom.

In the event that the model fails to converge using the unstructured covariance matrix, then only descriptive statistics will be presented.

Summary statistics (observed and change from Baseline, LS means with corresponding two-sided 95% confidence intervals (CIs), and p-values will be presented at each post-Baseline visit for the Full Analysis Set. The primary comparison is based on the LS mean change from Baseline to Week 16.

LS mean  $\pm$  SE from the MMRM model over time for the change from Baseline values will be displayed in line plots for the Full Analysis Set.

The above MMRM model will be used for each of the primary, secondary, and exploratory endpoints. CGI-I score will be analyzed using a similar MMRM model with effects for visit, Baseline CGI-S score, and Baseline CGI-S score-by-visit interaction. PGI-I score will be analyzed using an MMRM model with an effect for visit.

NPI-Q Caregiver and Distress scores will be summarized in shift tables to determine the number and percentage of subjects with Severity scores classified as none, mild, moderate, or severe relative to the same classification at the Baseline visit; and the number and percentage of subjects with Distress scores classified as not distressing at all, minimal, mild, moderate, severe, and extreme or very severe relative to the same classification at the Baseline visit. For the by-visit shift summary, the denominator is the number of subjects with non-missing values at Baseline and the given visit for the given parameter.

For each of the continuous efficacy endpoints (except for CGI-I and PGI-I) the null hypothesis is that the change from baseline to a certain time-point is equal to 0. The corresponding alternative hypothesis is that the change from baseline to a certain endpoint is not equal to 0.

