## 20.2 Schedule of Events and Assessments for ACP-103-063 (continued)

Period	Screening	Treatment						Safety Follow-up
		Baseline		16/EOT				
Visit Week	-5 to 0	0	2	4	8	12	16/EOT	20 a
Visit Number	1	2	3	4	5	6	7/ET b	8
Visit window (days)			±3	±3	±3	±3	±3	+4
Type of Visit	clinic	clinic	clinic	clinic	clinic	clinic	clinic	telephone
MDS-UPDRS Parts I and II (Patient)	X	X	X	X	X	X	X	
MDS-UPDRS Parts I and II (Caregiver)	X	X	X	X	X	X	X	
CGI-S specific to H&D	X	X	X	X	X	X	X	
CGI-I specific to H&D			X	X	X	X	X	
PGI-I specific to H&D			X	X	X	X	X	
VRFCAT	X	X		X			X	
Caregiver Strain Index	X	X	X	X	X	X	X	
Geriatric Depression Scale (Short Form)	X	X	X	X	X	X	X	
Concomitant medication	X	X	X	X	X	X	X	X
Assessment of adverse events		X	X	X	X	X	X	X
Dispense study drug		X	X	X	X	X		
Study drug return			X	X	X	X	X	
Study drug accountability			X	X	X	X	X	

Abbreviations: ADL=activities of daily living; BMI=body mass index; CGI-I=clinical global impression – improvement; CGI-S=clinical global impression – severity; C-SSRS=Columbia-Suicide Severity Rating Scale; ECG=electrocardiogram; EOT=end of trial; ET=early termination; FSQ= functional status questionnaire; H&D=hallucinations and delusions; MMSE=mini-mental state examination; NPI=neuropsychiatric inventory; NPI-Q=neuropsychiatric inventory – questionnaire; PGI-I=patient global impression – improvement; MDS-UPDRS=Movement Disorders Society – Unified Parkinson’s Disease Rating Scale; VRFCAT=virtual reality functional capacity assessment tool

a The safety follow-up telephone call visit is to occur 30 (+4) days after the last dose of study drug, nominally at Week 20 for completers and earlier for ET subjects.

b A subject terminating early should at a minimum complete assessments of safety (vital signs, ECG, AEs, clinical laboratories, C-SSRS) and, if possible, complete all Week 16 assessments.

- c The ECG may be repeated once at Screening in consultation with the Medical Monitor. ECGs can be performed any time before blood sampling or at least 30 minutes after blood sampling during clinic visits.
- d Vital signs (sitting or supine [ $>3$  minutes]) blood pressure, pulse rate, oral temperature, and respiratory rate) will be performed at Screening and each study visit.

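### CGI-S change is measured from a rating that had to be at least 4 for entry, so regression to the mean alone gives some improvement, and rejecting zero change is not evidence of a drug effect

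*SAP*

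**What the plan says.** **Entry rule.** Inclusion criterion 10 in Protocol 4.1 reads "Has a CGI-S score of ≥ 4 when assessing psychosis symptoms at Visit 1 (Screening) and Visit 2 (Baseline".

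**Reference value.** SAP 5.1: "Baseline is defined as the last non-missing value prior to the first dose of study drug". Protocol 9.5 has the same rule. SAP 3.1 adds: "The first dose of study drug (pimavanserin) should be taken on the morning of the day after the Baseline visit". The schedule in SAP 20.2 has a single row, "CGI-S specific to H&D", with one rating per visit. Unless there is an unscheduled rating, the Visit 2 score that admits the subject is also the score subtracted.

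**Endpoint and test.** SAP 12.2 lists as secondary "Change from Baseline to Week 16 on the CGI-S score for hallucinations and delusions". SAP 12.8 sets the null: "the null hypothesis is that the change from baseline to a certain time-point is equal to 0". Only CGI-I and PGI-I are excepted. Section 12.8 also asks for MMRM p-values at each post-Baseline visit and a paired t-test with last observation carried forward. SAP 5.1 sets a two-sided 0.05 level.

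**Statements the other way.** Protocol 9.2, SAP 12 and SAP 12.5 each say that no hypothesis testing is planned. SAP 3.3 confirms that there is one arm. Neither document mentions regression to the mean.

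**The concern.** CGI-S is a single clinician rating on a 7-point scale, so it carries rating error and short-term symptom fluctuation. Criterion 14 itself allows symptoms to be intermittent. A lower cut-off on such a rating admits subjects whose Baseline score happened to be high that day and turns away those whose score happened to be low. When the retained score is then subtracted from a Week 16 score that was not selected, the average difference is negative, which on this scale means improvement.

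Two features of the plan look protective but are not. Applying the threshold at two visits does not help, because the second application falls on the analysis baseline. Baseline adjustment in the MMRM does not help either, because the LS mean is evaluated at the mean of the selected baselines.

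At stake is how one secondary result is read. A small p-value for CGI-S change would be taken as clinician-rated benefit on psychosis, and Protocol 1.5 intends to relate such benefit to function. Part of that change could come from the entry rule alone.

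**Working it through.** **1. Planned numbers.** Protocol 3.1 gives 89 screened, 40% screen failure and 20% drop-out. 89 × 0.60 = 53.4 and 53 × 0.80 = 42.4, which agree with the stated 53 enrolled and 42 completers. No power, effect size, or CGI-S mean, SD or reliability is stated.

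**2. Model with no drug effect.** Rating at visit v: Y_v = T + e_v, rounded to an integer. T is stable true severity and e_v is independent error with mean 0. A subject enters if Y_Screening ≥ 4 and Y_Baseline ≥ 4. Before rounding,

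E[Y_16 − Y_Baseline | entry] = −E[e_Baseline | entry] < 0,

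because the cut-off retains positive Baseline errors and e_16 is not selected.

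**3. Size, main assumptions.** True severity in screened subjects has mean 4.0 to 5.0 and SD 0.8; single-rating reliability is 0.50, 0.64 or 0.76; n = 42; two-sided 0.05 t-test of change against zero. These inputs are assumed. Rows shown are those in which at least 60% pass the threshold, since the protocol's total screen failure is 40%.

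| Screened mean | Reliability | Pass | Mean change | Rejects zero |
|---|---|---|---|---|
| 4.0 | 0.76 | 61% | -0.10 | 15% |
| 4.5 | 0.50 | 70% | -0.17 | 15% |
| 4.5 | 0.64 | 76% | -0.10 | 10% |
| 4.5 | 0.76 | 80% | -0.06 | 8% |
| 5.0 | 0.50 | 84% | -0.10 | 8% |
| 5.0 | 0.64 | 89% | -0.05 | 7% |
| 5.0 | 0.76 | 92% | -0.03 | 5% |

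The range is -0.03 to -0.17 points and about 5 to 15%. Repeat runs move the rejection rates by about one percentage point.

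**4. Second set of assumptions.** Total SD 1.0 and test-retest correlation 0.5, 0.7 or 0.9 before rounding, with the screened mean chosen to fix the pass rate; n = 42.

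| Failing on CGI-S | Mean change | Rejects zero |
|---|---|---|
| 40% | -0.20 / -0.13 / -0.06 | 25 / 17 / 10% |
| 20% | -0.11 / -0.07 / -0.03 | 10 / 8 / 6% |
| 10% | -0.06 / -0.04 / -0.02 | 6.4 / 5.5 / 5.2% |

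The 40% row is a limiting case in which CGI-S alone uses up the whole screen-failure allowance. There, at correlation 0.5, 24.5 of the 24.6 percentage points of rejection are toward improvement. The carried-forward t-test can include drop-outs; with n = 53 the 40% row becomes 30 / 19 / 12%.

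**5. Hand check of one case.** With screened mean 4.5 and correlation 0.5, 75% pass, the mean change is -0.135 and the SD of change is 1.02. SE = 1.02/√42 = 0.157, and -0.135/0.157 = -0.86. With critical t of 2.02, P(reject) ≈ Φ(-2.02 + 0.86) + Φ(-2.02 − 0.86) = 0.123 + 0.002 = 0.125. The simulation gives 13%.

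**6. Isolating the cause.** If the threshold is applied at Screening only, the mean change is 0.00 and the t-test rejects in 4.6 to 5.2% of trials. Selection on the Baseline rating therefore accounts for the shift.

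**7. Not modelled.** Disease progression or informative drop-out could offset the shift, and open-label rating could add to it.

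**The case against.** **The test is valid for what it says.** This stands. The stated null is zero mean change, and selection makes the true mean change non-zero, so rejecting it is correct. A reader might infer that the test has lost its 5% error rate. For the literal null it has not. What fails is the step from rejection to a drug effect.

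**Every single-arm change has this limit.** Partly right: no before-after change here identifies a drug effect. This component is different because its direction is known and it comes from the plan's own one-sided entry rule on the outcome scale. Schwab and England is also used for entry (criterion 5), but with a 40 to 80% window, so the direction there is not fixed in the same way.

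**The size is assumed and may be small.** This stands. The 40% screen failure covers 14 active inclusion and 31 active exclusion criteria, so CGI-S probably takes only part of it, and the lower figures are then the relevant ones. Milder screened populations give much larger rejection rates, but they need more than 40% to fail on CGI-S alone, which the protocol's own figure does not allow.

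**The study is exploratory and disclaims testing.** True, and it limits the severity. SAP 12.8 nevertheless specifies hypotheses, p-values and t-tests.

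**Two further inferences lack support.** A reader might suppose that raters inflate scores to qualify subjects. The documents say nothing of this, and Protocol 3.1.1 describes a sponsor eligibility review. A reader might also treat CGI-I as a clean substitute. SAP 5.2.8 anchors it to symptoms at Baseline, so genuine fluctuation at that visit affects it too, and SAP 12.5 sets no hierarchy in which to move it.

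**Conclusion.** The point holds as an interpretive defect in one secondary endpoint. CGI-S change starts from a rating selected to be at least 4, so its expected value is below zero without treatment effect whenever ratings are less than perfectly reliable. The direction follows from the documents; the size does not.

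Under the main assumptions, the bias is at most about a sixth of a CGI-S point. The chance of a nominally significant change without drug effect is about 5 to 15%, and about 5 to 10% if no more than 20% of screened subjects fail on CGI-S. Lower reliability combined with CGI-S causing the entire 40% screen failure would raise that to about 25%, a limiting case. If nearly all screened subjects sit well above 4, or ratings are very stable, the effect is negligible.

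This does not show that the drug has no effect on psychosis, and it does not touch the primary mFSQ analysis. It should be corrected before database lock because the correction is simple and brings SAP 12.8 closer to the plan's own statements on testing.

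**What to change.** In SAP 12.8, for CGI-S change:

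- Remove the null of zero, the MMRM p-values and the paired t-test. This agrees with Protocol 9.2, SAP 12 and SAP 12.5.
- Keep the LS mean and 95% CI at each visit, labelled descriptive.
- Add one sentence, repeated as a footnote to the CGI-S table and plot: the change includes regression to the mean from the entry threshold at Baseline and is not by itself evidence of a drug effect. The sentence is needed even without p-values, because an interval that excludes zero invites the same reading.
- Record the removal in the SAP's version history.

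The cost is a few lines of SAP text and small edits to the table shells, with no new data or analysis. The downside is that the CGI-S result will read slightly less favourably.

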## 13 SAFETY ANALYSES

All safety analyses will be performed using the actual treatment for the Safety Analysis Set using descriptive statistics.

### 13.1 Adverse Events

All adverse events (AEs) will be coded using MedDRA version 23.0 or higher.

An AE (classified by preferred term) will be considered a treatment-emergent AE (TEAE) if it started after the first dose of study drug and no later than the last study drug dose date + 30. AEs reported on Day 1 based on Baseline (pre-dose) findings (e.g., laboratory test results or ECG parameters) will not be considered as TEAEs.

For the following summaries, the event counts and the number and percentage of subjects reporting TEAEs will be tabulated:

- TEAEs by SOC and preferred term (PT)
- Most frequently reported TEAEs by SOC and PT
- TEAEs by PT
- TEAEs by maximum severity, SOC, and PT
  - if more than 1 AE occurs with the same PT for the same subject, the subject will be counted only once for that PT using the most severe occurrence
- TEAEs related to study drug by SOC and PT
- Treatment-emergent serious adverse events (TESAEs) by SOC and PT
- TEAEs leading to study drug discontinuation or study termination by SOC and PT
- AEs with fatal outcome by SOC and PT
- TEAEs with fatal outcome (that occurred within 30 days of last dose) by SOC and PT

The relationship of selected AEs to COVID-19 will be assessed as detailed in the DMP, Appendix B. COVID-19 related TEAEs will be tabulated separately.

For tabulations that include SOC and PT the display will be sorted alphabetically by SOC and then by descending subject frequency for the PTs within each SOC. SOCs will not be included in the TEAEs by PT tabulation. This display will be sorted by descending subject frequency.

An AE listing by subject will display all events, including those which are not treatment-emergent, and will include the verbatim term in addition to the MedDRA SOC and PT. This listing will also include all relevant eCRF data associated with the event: e.g. date of onset, date resolved, date of the first and last dose of study drug, severity, frequency, outcome, relationship to study drug, action taken with study drug, and required therapy. When a date is presented, the study day associated with the date will also be displayed. Separate listings will be presented for subjects with SAEs, subjects with TEAEs leading to study drug discontinuation or study termination, subjects who died (if any), and COVID-19 related AEs. In these listings, an indicator for TEAEs will also be included.

## 13.2 Other Safety Analyses

### 13.2.1 Clinical Laboratory Variables

Clinical laboratory tests are performed at Screening, Baseline, Week 4, and Week 16/ET visits. All laboratory test results are from a central laboratory. All units will be displayed in Système International [SI] units.

